65	6.5.1 Visit 25	--	
 • Review lab results from prior visit 
 ○ For subjects exhibiting an increase in ALT or AST (>3 x ULN) or total bilirubin (>2 x ULN) at the prior visit, follow the instructions in Section Error! Reference source not found. • Assess clinically for liver dysfunction (symptoms, signs [if a clinic visit]) as directed by the checklist in Appendix 4 (Section Error! Reference source not found.). 	Details new procedures for Visit 25
66	6.5.3 Visit 27 (End of Study Visit)	Visit 27 is the last visit in this study and will occur 28±3 days after the last dose of study drug (Visit 24).	Visit 27 is the last visit in this study and will occur 28±3 days after the last dose of study drug (Visit 24). The visit will be conducted in the clinic.	Adds that this visit is in-clinic
67	7.2.1 Specific Gravity and Urine Osmolality	They will bring that specimen to their clinic visit where specific gravity will be measured by dipstick using an automated device in the clinic.	They will either bring that specimen to their clinic visit or provide to a HHC if a remote visit is conducted , where specific gravity will be measured by dipstick using an automated device in the clinic .	Updates procedures for specific gravity

Page	Section	Version 2 dated June 18, 2020	Version 3	Explanation
69	7.3.4 Vital Sign Measurements	Subjects will remain at rest in a seated position for...	Subjects will remain at rest in a seated position for... Although sitting is the standard position for measurement of vital signs, a site that uses a different standard of care, e.g. semi-recumbent, may utilize that position as long as all measurements at that site are done in the same position. Other positions to obtain vital signs may be used after discussion with the medical monitor.	Allows for positions other than seated for vital signs under certain circumstances.
69	7.3.4 Vital Sign Measurements	... Any confirmed, clinically significant vital sign measurements must be recorded as an AE.	Any confirmed, clinically significant vital sign measurements must be recorded as Medical History during the Screening and Baseline Periods and as an AE after the start of study drug.	Specifies when CS vital signs should be recorded as AEs
70	7.3.5 12-Lead ECGs	All CS findings will be reported as AEs.	All CS findings will be reported as Medical History during the Screening and Baseline Periods and as AEs after the start of study drug.	Specifies when CS ECGs should be recorded as AEs
73	7.3.7.2 Changes in Study Drug Dosing if Liver Chemistry Test Abnormalities Occur...	-	Liver chemistry test increases of a lesser extent should be discussed with the medical monitor. They may be related to the underlying variability of such tests in ADPKD patients. Generally, dosing should continue, but the frequency of laboratory testing should increase, particularly during the Maintenance Period. Slowing of titration may also be considered if the abnormalities occur during the Titration Period.	Additional instructions for handling liver chemistry test increases that are below the threshold of >3 x ULN for transaminases or >2 x ULN for total bilirubin.
74	7.3.8.2 Eliciting and Documenting AEs and SAEs	Other changes in health or new symptoms occurring during the	Other changes in health or new symptoms occurring during the	Adds the Baseline Period to record AEs and SAEs

Page	Section	Version 2 dated June 18, 2020	Version 3	Explanation
		screening period will be recorded as medical history.	s Screening or Baseline p Periods will be recorded as medical history.	
75	7.3.8.3 Reporting AEs, SAEs, and AEs of Special Interest	Any medical condition that is present at the time the subject is screened, i.e., medical history, but does not deteriorate should not be reported as an AE.	Any medical condition that is present at the time the subject is screened or during baseline , i.e., medical history, but does not deteriorate should not be reported as an AE.	Adds the Baseline Period to statement
77	7.3.8.8 Pregnancy	Pregnancy is not regarded as an AE unless there is a medical/surgical complication. Any pregnancy that occurs during study participation must be reported as an AESI using a clinical study pregnancy reporting form. To ensure subject safety, each pregnancy must be reported through this mechanism to ICON PVSS within 24 hours of learning of its occurrence.	Pregnancy is not regarded as an AE unless there is a medical/surgical complication. Any pregnancy of a subject or the partner of a subject that occurs during study participation must be reported as an AESI using a clinical study pregnancy reporting form. To ensure subject safety, each pregnancy must be reported through this mechanism to ICON PVSS within 24 hours of learning of its occurrence.	Adds that pregnancies in partners of subjects will be followed like pregnancies in subjects.
78	7.3.10 HERC	-	The HERC will also assess the relationship to tolvaptan of prior instances of liver dysfunction and liver chemistry test abnormalities that occurred while enrolled subjects were previously receiving tolvaptan.	Additional assessment by HERC
80	8.4.1 Primary Hepatic Safety Endpoint	Descriptive statistics (n, percentage, 95% confidence interval) will be used to summarize the proportion of subjects who develop ALT levels >3 x ULN that were assessed by the Investigator in consultation with the medical monitor and sponsor and adjudicated by the independent HERC to be related to lixivaptan and resulted	Descriptive statistics (n, percentage, 95% confidence interval) will be used to summarize the proportion of subjects who develop ALT levels >3 x ULN that were assessed by the Investigator in consultation with the medical monitor and sponsor and adjudicated by the independent HERC to be at least probably related to lixivaptan and	Updates primary endpoint to match other instances in the protocol.

Page	Section	Version 2 dated June 18, 2020	Version 3	Explanation
		in discontinuation of the study drug during the Titration and Maintenance Periods.	resulted in discontinuation of the study drug during the Titration and or Maintenance Periods.	
80-81	8.4.2 Secondary Hepatic Safety Endpoints	
Similarly, descriptive statistics (n, percentage, 95% confidence interval) will be utilized to present the 2 secondary endpoints:
 
The proportion of subjects who develop ALT levels >5 x ULN that were assessed by the Investigator in consultation with the medical monitor and sponsor and adjudicated by the independent HERC to be related to lixivaptan and resulted in discontinuation of the study drug during the Titration and Maintenance Periods; and
 
The proportion of subjects who develop ALT levels >3 x ULN that were assessed by the Investigator in consultation with the medical monitor and sponsor and adjudicated by the independent HERC to be related to lixivaptan and resulted in lixivaptan dose reduction during the Titration and Maintenance Periods
	
Similarly, descriptive statistics (n, percentage, 95% confidence interval) will be utilized to present the 2 secondary endpoints:
 
The proportion of subjects who develop ALT levels >5 x ULN that were assessed by the Investigator in consultation with the medical monitor and sponsor and adjudicated by the independent HERC to be at least probably related to lixivaptan and resulted in discontinuation of the study drug during the Titration and or Maintenance Periods; and
 
The proportion of subjects who develop ALT levels >3 x ULN that were assessed by the Investigator in consultation with the medical monitor and sponsor and adjudicated by the independent HERC to be at least possibly related to lixivaptan and resulted in lixivaptan dose reduction during the Titration and or Maintenance Periods
	Updates the secondary endpoints to match other instances in the protocol.

Page	Section	Version 2 dated June 18, 2020	Version 3	Explanation
85	9.3 Subject Information and Consent	A written informed consent [...] shall be obtained from each subject before entering the study or performing any unusual or non-routine procedure [...]. Informed consent templates may [...]	A W ritten informed consents [...] shall be obtained from each subject before entering the study, upon re-screening, and when or performing any unusual or non-routine procedure [...]. An informed consent templates may [...]	Adds the need to have a new ICF for re-screening
89	11.1.1 Monitoring of the Study	In doing so, the Monitor will visit the Investigator and study site at periodic intervals, in addition to maintaining necessary telephone and letter contact.	In doing so, the Monitor will visit the Investigator and study site at periodic intervals, or conduct central or remote monitoring , in addition to maintaining necessary telephone, email and letter contact.	Changes the study monitoring procedures due to remote visits
95	13.4 Appendix 3: Additional Potential Hepatic Testing...	--	
 • Clinical chemistry: 
 ○ Glutamate dehydrogenase (GLDH) 	Addition of newly described liver chemistry test
96-97	13.4 Appendix 4: Liver Dysfunction Checklist	--	Adds Appendix 4	Adds Liver Dysfunction Checklist, a form to be completed for both remote and clinic visits with associated instructions.

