7.3.8 Adverse Events

7.3.8.1 Definitions of Adverse Events

The Investigator is responsible for reporting all AEs that are observed or reported during the study, regardless of their relationship to study drug or their clinical significance, as outlined in [Section 7.3.8.2](#) below.

An AE is defined as any untoward medical occurrence in a subject enrolled into this study regardless of its causal relationship to study drug.

A treatment-emergent AE (TEAE) is defined as any event not present before exposure to study drug or any event already present that worsens in either intensity or frequency after exposure to study drug.

An SAE is defined as any event that results in death, is immediately life threatening, requires in-subject hospitalization or prolongation of existing hospitalization, results in persistent or significant disability/incapacity, or is a congenital anomaly/birth defect. Important medical events that may not result in death, be life threatening, or require hospitalization may be considered SAEs when, based upon appropriate medical judgment, they may jeopardize the subject or may require medical or surgical intervention to prevent one of the outcomes listed in this definition.

Hospitalization does not include admissions for treatment of a pre-existing condition, including surgery, not associated with a new AE; respite care; social reasons; administrative reasons; skilled nursing care; rehabilitation; hospice; or same-day surgery.

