7.3.8.2 Eliciting and Documenting Adverse Events and Serious Adverse Events

All SAEs will be recorded from the time the ICF is signed until study completion. Non-serious AEs will be recorded from the start of study treatment until study completion. Other changes in health or new symptoms occurring during the Screening or Baseline Periods will be recorded as medical history.

At every study visit, subjects will be asked a standard non-leading question to elicit any medically related changes in their well-being. They will also be asked if they have been hospitalized, had any accidents, used any new medications, or changed concomitant medication regimens (both prescription and over-the-counter medications).

In addition to subject observations, any abnormal laboratory test results (hematology, clinical chemistry, or urinalysis) or other safety assessments (e.g., ECGs, radiological scans, vital sign measurements, physical examination findings), including those that worsen from baseline, deemed to be CS in the medical and scientific judgment of the Investigator are to be recorded as AEs or SAEs.

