13.4 Appendix 4: Liver Dysfunction Checklist

The following items will be included in a checklist to be completed by the HHC for remote visits (Part 1 only) and by the site for clinic visits (Part 1 and Part 2) when directed by the protocol. For remote visits where there are findings on Part 1 of the checklist, telemedicine will be utilized to determine if a clinic visit is needed to complete Part 2.

Part 1 - Symptoms

Did the subject develop the following symptoms since the last visit?

Symptom
Fatigue
Weakness
Malaise
Loss of appetite
Nausea
Vomiting
Pain in the right upper part of the abdomen
Urine darker than usual
Itching
Yellowing of skin
Yellowing of eyes
Fever
Rash

Part 2 - Signs

Did the subject develop the following signs since the last visit?

Sign
Jaundice
Ascites
Rash
Fever
Right upper quadrant tenderness or liver enlargement
Encephalopathy

Any symptoms, signs, or an associated diagnosis deemed clinically significant based on information entered in Part 1 or Part 2 during either a remote visit or a clinic visit will be entered in the eCRF by the site as adverse events. The Investigator will determine whether a constellation of symptoms and signs in the context of all available information including

laboratory data indicate the potential presence of liver dysfunction. Otherwise, individual symptoms and signs need to be recorded as other AEs or as an alternative diagnosis. *For example*, fatigue alone may be a non-specific AE with no clear cause. *As another example*, fatigue, weakness, and vomiting occurring together may indicate a gastroenteritis. Liver dysfunction should only be considered when the totality of the evidence makes that a plausible diagnosis.

If liver dysfunction is suspected, the Investigator will communicate with the medical monitor and additional testing detailed in [Section 7.3.7.1](#) may be recommended. Those tests are listed in Appendix 3 (Section 13.3). Additionally, the following supplemental information to complete the liver dysfunction eCRF will be collected by the site:

- Was there evidence of a concomitant viral illness?
- Did the subject's alcohol intake increase since the previous visit? If so,
 - on what date did it start?;
 - on what date did it end?;
 - what type of alcohol was ingested?; and
 - what was the total daily alcohol intake during this time?

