11.4 Appendix IV: List of Tables, Listings, and Figures

List of Tables, Listings, Figures Listing 16.2.1.1 Subject Disposition All Subjects Listing 16.2.2 Protocol Deviations All Subjects Listing 16.2.4.1 Demographic Characteristics All Subjects Listing 16.2.4.2.1 Baseline Characteristics - eGFR All Subjects Listing 16.2.4.2.2 Baseline Characteristics - ALT, AST and Total Bilirubin All Subjects Listing 16.2.4.3 Medical History All Subjects Listing 16.2.4.4 Concomitant Procedures All Subjects Listing 16.2.4.5 Medical History of Autosomal Dominant Polycystic Kidney Disease (ADPKD) All Subjects Listing 16.2.4.6 Prior and Concomitant Medications All Subjects Listing 16.2.5.1 Drug Accountability Safety Population Listing 16.2.5.2 Drug Tolerability/Modification Safety Population Listing 16.2.6.1 Listing of Serum Creatinine and estimated Glomerular Filtration Rate (eGFR) All Subjects Listing 16.2.7.1.1 Liver Dysfunction Details All Subjects Listing 16.2.7.1.2 Potential Hepatic Events All Subjects Listing 16.2.7.2 Criteria for Primary and Secondary Hepatic Safety Endpoints All Subjects Listing 16.2.7.3 Adverse Events All Subjects Listing 16.2.8.1.1 Laboratory Test Results - Hematology All Subjects Listing 16.2.8.1.2.1 Laboratory Test Results - Chemistry All Subjects Listing 16.2.8.1.3 Laboratory Test Results - Liver Chemistry All Subjects Listing 16.2.8.1.4 Laboratory Test Results - Urinalysis All Subjects Listing 16.2.8.1.6 Additional Potential Hepatic Testing All Subjects Listing 16.2.9.1 Vital Signs Results All Subjects Listing 16.2.10 .1 Electrocardiogram (ECG) Results All Subjects Listing 16.2.12 Pregnancy Results All Female Subject Table 14.1.1.1 Summary of Subject Disposition All Subjects Table 14.1.1.4 Summary of Protocol Deviation Enrolled Population Table 14.1.2.1.1 Summary of Demographic Characteristics Enrolled Population Table 14.1.2.2.1 Summary of Baseline Disease Characteristics Enrolled Population Table 14.1.5.1 Summary of Study Drug Exposure Safety Population Table 14.3.1.1.1 Overall Summary of Treatment Emergent Adverse Events (TEAEs) Safety Population Table 14.3.1.2.1 Summary of TEAEs by System Organ Class and Preferred Term Safety Population Table 14.3.1.2.2.1 Summary of Serious TEAEs by System Organ Class and Preferred Term Safety Population Table 14.3.1.2.2.2 Summary of Non-serious TEAEs by System Organ Class and Preferred Term Safety Population Table 14.3.1.2.4 Summary of Adverse Event of Special Interest by System Organ Class and Preferred Term Safety Population Table 14.3.2.1 Summary of Liver Chemistry Abnormalities Defined as Primary and Secondary Hepatic Safety **Endpoints Safety Population** Table 14.3.5.4 Summary of Post-Baseline QTcF Safety Population

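### Appendix 4's clinical-significance condition on checklist symptoms conflicts with Sections 7.3.8.1 and 7.3.7.3, so sites can apply different recording thresholds to the same symptom

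*Protocol*

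**What the plan says.** Protocol Appendix 4 (Section 13.4) is a liver dysfunction checklist with 13 symptoms in Part 1 and 6 signs in Part 2. Its instructions say what the site enters in the eCRF as adverse events: "Any symptoms, signs, or an associated diagnosis deemed clinically significant based on information entered in Part 1 or Part 2". The investigator then judges whether the findings together point to liver dysfunction, and the paragraph continues: "Otherwise, individual symptoms and signs need to be recorded as other AEs or as an alternative diagnosis". One of its examples is that "fatigue alone may be a non-specific AE with no clear cause".

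Three other protocol sections bear on the same findings:

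- **Section 7.3.8.1** makes the investigator responsible for "reporting all AEs that are observed or reported during the study, regardless of their relationship to study drug or their clinical significance". Its definition reads: "An AE is defined as any untoward medical occurrence in a subject enrolled into this study regardless of its causal relationship to study drug".
- **Section 7.3.8.2** does apply a clinical-significance test, but to a different class of finding: "In addition to subject observations, any abnormal laboratory test results" and other safety assessments such as ECGs and vital signs.
- **Section 7.3.7.3** requires a report within 24 hours, through the SAE pathway, for a subject with any sign or symptom of hepatic dysfunction. It refers to Appendix 4 and sets no significance condition.

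SAP Section 8.6.5 defines a TEAE without reference to clinical significance, so the tables hold whatever sites entered. SAP Section 9 cuts the output after early termination, but Appendix IV keeps the overall TEAE summary, the TEAE table by system organ class and preferred term, the AESI table and "Summary of Non-serious TEAEs by System Organ Class and Preferred Term".

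**The concern.** AEs are a secondary safety endpoint, and in a hepatic safety study the checklist items are the symptoms a reader will look for. A significance filter suits laboratory values, ECGs and examination findings, where small deviations are common and carry little meaning. A symptom the subject reports is different: under the protocol's own definition it is an AE once it is an untoward occurrence.

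If the filter is applied to symptoms, the count depends on how the symptom came to light. Mild nausea volunteered in answer to the open question at each visit is an AE. The same nausea reported only on the checklist may not be entered. It also depends on which sentence a site follows. Any departure runs one way, towards fewer recorded events. The study is open-label, not randomized and has a single arm (Sections 5.4 and 5.5), so no comparator would reveal it.

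**Working it through.** The plan gives no figure on this point. The check is therefore a comparison of texts, using one case: new mild nausea after dosing, reported only on the checklist, with no other finding, and judged not clinically significant.

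| Text | Is it recorded? |
|---|---|
| Section 7.3.8.1 | Yes, as an AE; clinical significance is expressly irrelevant |
| Section 7.3.8.2 | The significance test covers laboratory and other safety assessments, listed in addition to what subjects report; it does not reach the nausea |
| Appendix 4, opening recording sentence | Not required, because the condition is not met |
| Appendix 4, later sentence | Yes, if it covers all symptoms; no, if it only sorts the significant ones into liver and non-liver events |
| Section 7.3.7.3 | An AESI report, if any Appendix 4 item counts; none, if read with the advice in Appendix 4 to consider liver dysfunction only when the whole evidence makes it plausible |

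So one checklist answer can be an AESI, an ordinary AE or nothing on the AE page, each with some support in the current text.

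**Is the filter on symptoms an exception?** Yes. Elsewhere the protocol applies the test to examination findings (7.3.3), vital signs (7.3.4), ECGs (7.3.5), and laboratory and other safety assessments (7.3.8.2, 7.3.9). Appendix 4 alone applies it to symptoms.

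**Is there another eCRF route for the symptom?** Appendix 4 describes the supplemental liver dysfunction eCRF information for cases where liver dysfunction is suspected. For an isolated symptom without that suspicion, it describes only the AE page.

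**How often does the question arise?** A subject who completes treatment and attends Visit 25 has the checklist at 3 to 6 titration visits, 13 visits from Visit 12 to Visit 24, and Visit 25: 3 + 13 + 1 = 17 to 6 + 13 + 1 = 20 visits. This counts occasions for the choice, not events lost. The documents give neither the rate of positive answers nor the share judged not significant.

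**What could one omission do to a table?** The Safety Population includes at least the 6 subjects who entered the Maintenance Period, so omitting a subject's only event of a given term lowers that percentage by at most 1/6 = 16.7 points. At the planned maximum of 50 treated subjects it would be 1/50 = 2.0 points.

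**The case against.** The strongest reply is that Appendix 4 says significant findings are entered; it does not say that others are left out. The same paragraph directs individual symptoms to other AEs, and a symptom recorded under a diagnosis such as gastroenteritis still appears in the TEAE tables. Section 7.3.8.1 covers anything observed or reported, and a positive checklist answer is a report. Every visit also has a non-leading AE question, and AE review is a task separate from the checklist.

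Much of this stands. A reader might infer that the plan allows checklist symptoms to become AEs only if significant, so that TEAEs are necessarily missing. The documents do not support that: the restriction is one reading of one sentence. But the later sentence has an unclear scope, and the open question catches what subjects volunteer, whereas a checklist exists to catch what they do not.

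Three further inferences also go too far:

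- *Liver injury would go undetected.* Section 7.3.7 calls for prompt liver tests on any suspicious Appendix 4 symptom or sign, whatever the AE page says. The primary endpoint rests on ALT, committee adjudication and discontinuation. The Liver Dysfunction Details listing is also retained.
- *The investigator must judge significance before the liver panel is back.* The protocol does not fix when the AE decision is made, results from the prior visit are reviewed, and Visit 25 draws serum creatinine only.
- *The planned analysis of aminotransferase elevation with symptoms is damaged.* Protocol Section 8.4.3 and SAP Section 8.6.3 do not state its data source, and its swimmer plot is not in the reduced output.

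**Conclusion.** The point holds as a conflict between instructions. Appendix 4, Section 7.3.8.1 and Section 7.3.7.3 set different thresholds for the same checklist finding, and nothing ranks them. Under-recording of mild on-drug symptoms in the retained TEAE tables is a possible result, at sites that apply the opening Appendix 4 sentence literally. It is not a certain result of the plan.

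No number of lost events can be given, and any percentage would be invention. In absolute terms the effect is small: 6 subjects entered the Maintenance Period and most of them ended early. A percentage in so small a table is still sensitive to a single omission. The conclusion assumes that some symptoms come to light only through the checklist and that some sites read the significance condition as a filter. The documents neither confirm nor exclude either.

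**What to change.** Reconcile Appendix 4, Section 7.3.8.1 and Section 7.3.7.3 under one rule:

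1. In Appendix 4, remove the clinical-significance condition for subject-reported symptoms and state: *Every new or worsened checklist symptom is recorded as an AE under Section 7.3.8.1, either as the symptom or under its unifying diagnosis.* The condition may stay for findings that are signs only.
2. State that items on both lists follow the symptom rule whichever part captures them: fever, rash, and yellowing of skin or eyes with jaundice. Otherwise the same rash would be an automatic AE under Part 1 and a filtered one under Part 2.
3. State in Section 7.3.7.3 and Appendix 4 which checklist findings are also AESIs, so that the 24-hour trigger and the whole-evidence advice no longer compete.
4. Enter the completed checklist responses, with onset dates, in the eCRF.

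For the terminated study, the practical equivalent is to check the completed checklists against the AE listing (Listing 16.2.7.3), resolve differences by query, and state in the synoptic report which recording rule sites followed.

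The cost is a few sentences of protocol text, data entry from a form already completed, and a slightly higher count of mild AEs.
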